5.4.14.2. Time to Flare

Time to on-treatment flare and time to off-treatment flare will be summarized for each type of flare by intervention arm separately.

Time to on-treatment flare will be defined as the number of days between the date of first study intervention intake and the date of the first occurrence of on-treatment flare (i.e. the date of the first on-treatment flare of each type- the date of first study intervention intake +1). The participants who withdrew early from the study before experiencing on-treatment flare or who did not experience on-treatment flare will be censored at the last available blood markers or liver enzymes assessment at or before EOT.

Time to off-treatment flare will be defined as the number of days between the date of last study intervention intake and the date of the first occurrence of off-treatment flare (i.e. the date of experiencing the first off-treatment flare of each type- the date of last study intervention intake). The participants who withdrew early from the study before experiencing off-treatment flare or who

did not experience off-treatment flare will be censored at the last available blood markers or liver enzymes assessment.

The Kaplan-Meier method will be used to estimate and plot the cumulative incidence by each intervention arm. The log-rank test will be performed to compare among the intervention arms. The median time with 90% CI will be estimated using Kaplan-Meier method. In addition, the hazard ratio and the corresponding 90% confidence interval will be estimated based on a stratified Cox's regression model by the 2 randomization stratification factors. In addition, the number and percentage of participants who had an event or were censored will be reported by intervention arm.

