	last visit in double-blind phase	49 ^a	EOT ^a	

^a End of treatment (EOT) visit will be the last post-baseline visit in double-blind phase.

b) **Follow-Up Phase**

Analysis phase (FU)	Target day	Analysis time point (Week)	Analysis time point (label)	Time interval (days) ^a (Arm 1-5 and Arm 6 [NA stopped])	Time interval (days) ^a (Arm 6 [NA continued])
Follow-up ^a	15	50	Follow-up Week 2	[1, 22]	
	29	52	Follow-up Week 4	[23,36]	
	43	54	Follow-up Week 6	[37,50]	
	57	56	Follow-up Week 8	[51, 71]	
	85	60	Follow-up Week 12	[72, 99]	[1, 99]
	113	64	Follow-up Week 16	[100, 127]	
	141	68	Follow-up Week 20	[128, 155]	
	169	72	Follow-up Week 24	[156, 190]	[100, 190]
	197	76	Follow-up Week 28	[191, 204]	
	211	78	Follow-up Week 30	[205, 218]	
	225	80	Follow-up Week 32	[219, 232]	
	253	84	Follow-up Week 36	[233, 274]	[191, 274]
	281	88	Follow-up Week 40	[275, 288]	
	295	90	Follow-up Week 42	[289, 302]	
	309	92	Follow-up Week 44	[303, 316]	
	337	96	Follow-up Week 48	[317, $+\infty$]	[275, $+\infty$]

c) Extended Follow-Up Phase

Analysis phase (EFU)	Target day	Analysis time point (Week)	Analysis time point (label)	Time interval (days) ^a
Extended Follow-up	15	102	Ext Follow-up Week 2	[1, 22]
	29	104	Ext Follow-up Week 4	[23, 36]
	43	106	Ext Follow-up Week 6	[37, 50]
	57	108	Ext Follow-up Week 8	[51, 71]
	85	112	Ext Follow-up Week 12	[72, 99]
	113	116	Ext Follow-up Week 16	[100, 127]
	141	120	Ext Follow-up Week 20	[128, 155]
	169	124	Ext Follow-up Week 24	[156, 190]
	197	128	Ext Follow-up Week 28	[191, 204]
	211	130	Ext Follow-up Week 30	[205, 218]
	225	132	Ext Follow-up Week 32	[219, 232]
	253	136	Ext Follow-up Week 36	[233, 274]
	281	140	Ext Follow-up Week 40	[275, 288]
	295	142	Ext Follow-up Week 42	[289, 302]
	309	144	Ext Follow-up Week 44	[303, 316]
	337	148	Ext Follow-up Week 48	[317, +∞]
	last visit in the study	999 ^a	EOS ^a	

^a End of study (EOS) visit (last available data during the extended follow-up) will be the last visit in the study.

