5.4.1. HBsAg Seroconversion

HBsAg seroclearance will be evaluated over all time points when assessed, with emphasis at the following time points:

- at Week 48
- at Week 96 (ie, 48 weeks after completion of all study interventions at Week 48) without restarting NA treatment,

- 12 weeks after stopping all study interventions (regardless when intervention was stopped) without restarting NA treatment, and
- 24 weeks after stopping all study interventions (regardless when intervention was stopped) without restarting NA treatment, and
- 36 weeks after stopping all study interventions (regardless when intervention was stopped) without restarting NA treatment, and
- 48 weeks after stopping all study interventions (regardless when intervention was stopped) without restarting NA treatment

Proportions at the time points listed in the above bullets will be analyzed using the Mantel-Haenszel test and 90% CIs stratified for treatment history status and screening HBeAg status.

5.4.1.1. At Week 48 and At Week 96

The proportion of participants achieving HBsAg seroclearance at EOT (Week 48), and at Week 96 (48 weeks after completion of all study interventions at Week 48) will be summarized by intervention arm. A participant will be defined as responder at Week 96 (with HBsAg seroclearance 48 weeks after completion of all study intervention at Week 48) if he/she has completed 48 weeks of treatment AND met the criteria for stopping NA treatment at Week 48 AND not required NA re-treatment between Week 48 and Week 96 AND had HBsAg seroclearance at Week 96. If the HBsAg value at Week 96 is missing, the LOCF approach will be used with the condition that no value earlier than Week 84 may be carried forward.

Those participants who did not meet the NA stopping criteria at Week 48 OR did not complete 48 weeks of treatment OR did not reach seroclearance at Week 96 will be defined as non-responders for Week 96. The participants who has no HBsAg value between Week 84 and 96 or required NA re-treatment prior to Week 96 will be considered as non-responder as well.

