A clinical flare occurs when a virologic flare and biochemical flare overlap in time. However, if there is no overlap in time, a clinical flare occurs when a virologic flare ends prior to a biochemical flare starting, and the end date of the virologic flare is within 4 weeks of the biochemical flare start date. The start date of a clinical flare is defined as the minimum start date of the virologic flare and the biochemical flare. The end date of a clinical flare is defined as the maximum end date of the virologic flare and biochemical flare, e.g., the later date of HBV DNA ≤ 200 IU/mL and 50% reduction from the peak ALT and/or AST level & $<3x$ ULN.

** Confirmed means that the criterion should be fulfilled at 2 or more consecutive time points or at the last observed time point.

The virologic and clinical flares will be assessed only off-treatment, while biochemical flares will be identified on treatment and off treatment, respectively. On-treatment virologic flares are described as virologic breakthrough in Section 5.4.15.1. On-treatment will be defined as the time period in which the participant receives any of the study interventions. Off-treatment will be defined as the time period after stopping all study interventions (including NA).

The incidence rate will be calculated and summarized for each type of on-treatment or off-treatment flares (virologic, biochemical and clinical) separately, as well as the overall incidence of participants experiencing at least one flare, regardless of type, by study intervention arm. Additionally, for each participant the total number of flares the participant experienced will be counted by type and overall, respectively. Such counts will be used to summarize the distribution of the total number of flares both by type and across types by intervention arm.

For on-treatment biochemical flares, the incidence of flares causing treatment discontinuation will be summarized by intervention arm. Further, for off-treatment flares, the count and percentage of participants who experienced a flare followed by NA re-treatment will be summarized by flare type and intervention arm. Similarly, the incidence of flares followed by the achievement of HBsAg seroclearance (at any time) will be summarized by flare type and intervention arm.

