5.4.15. Virologic Breakthrough

5.4.15.1. Definition

HBV virological breakthrough is defined as having a confirmed on-treatment HBV DNA increase by $>1 \log_{10}$ from nadir level (lowest level reached during treatment) in participants who did not have on-treatment HBV DNA level below the lower limit of quantification (LLOQ) or a confirmed on-treatment HBV DNA level $>200 \text{ IU/mL}$ in participants who had on-treatment HBV DNA level below the lower limit of quantification (LLOQ). Confirmed HBV DNA increase/level means that the criterion should be fulfilled at 2 or more consecutive time points or at the last observed time point.

On-treatment will be defined as the time period in which the participant receives any of the study interventions (including NA).

The number and proportion of participants who experience a virologic breakthrough will be summarized descriptively by intervention arm and analysis phase.

The number and proportion of participants who experience a virologic breakthrough followed by on-treatment biochemical flare will be summarized descriptively by intervention arm.

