5.4.15.2. Time to Virologic Breakthrough

Time to HBV virologic breakthrough will be defined as the number of days between the date of first study intervention intake and the date of the first occurrence of virologic breakthrough (i.e. the date of the first virologic breakthrough - the date of first study intervention intake +1). The participants who withdrew early from the study before experiencing virologic breakthrough or who did not experience virologic breakthrough will be censored at the last available HBV DNA assessment at or before EOT.

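### Read literally, time to on-treatment biochemical flare and time to virologic breakthrough count events on NA after Week 48 but censor event-free participants by EOT, so one late event can take an arm's Kaplan-Meier curve to 100%

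*SAP*

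**What the plan says.** - **Treatment window.** SAP 5.4.14.1: "On-treatment will be defined as the time period in which the participant receives any of the study interventions". Off-treatment begins only when everything, NA included, has been stopped. SAP 5.4.15.1 uses the same on-treatment window for breakthrough and names NA in it.
- **Flare types.** SAP 5.4.14.1: "The virologic and clinical flares will be assessed only off-treatment, while biochemical flares will be identified on treatment and off treatment". In 5.4.14.2 the on-treatment analysis therefore concerns biochemical flare only.
- **Event time.** In both 5.4.14.2 and 5.4.15.2 the event is the first occurrence, counted from first intake, with no upper limit.
- **Censoring.** For flare, participants who "did not experience on-treatment flare will be censored at the last available blood markers or liver enzymes assessment at or before EOT". For breakthrough, those who "did not experience virologic breakthrough will be censored at the last available HBV DNA assessment at or before EOT".
- **EOT.** Footnote to SAP Table 2: "End of treatment (EOT) visit will be the last post-baseline visit in double-blind phase". SAP 5.4.1.1 equates EOT with Week 48, whose analysis window closes on study day 350.
- **NA after Week 48.** Under Protocol 6.6, participants who miss the completion criteria stay on NA during follow-up.
- **Methods.** Kaplan-Meier curves, medians, log-rank tests and stratified Cox models apply to flare (5.4.14.2) and, through 5.4.11, to breakthrough.

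**The concern.** The event rule and the censoring rule use different windows. A participant still on NA in follow-up is on-treatment by definition, so a first biochemical flare or breakthrough then is an event dated after Week 48. A participant on NA without such an event is censored by EOT, although followed and tested at later visits. Past an arm's last EOT day, membership of the risk set depends on a future outcome: only people who will have the event remain.

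At stake are the tail of each cumulative incidence curve, the median time and, to a lesser degree, the log-rank and Cox comparisons, which take in these late event times.

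**Working it through.** The plan gives no figure for these endpoints, so there is none to reproduce. Arm sizes (90 in Arms 1 to 4, 45 in Arms 5 and 6) are from Protocol 9.2. Event counts and on-NA risks are assumptions.

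**Step 1: the algebra.** The product-limit estimate is S(t) = product of (1 − d/n) over event times, with d events among n at risk. After an arm's last EOT day, n equals the number of participants whose event is still to come. At the last event d = n, the factor is 0 and 1 − S = 100%, whatever the arm size.

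**Step 2: an example.** Four events before Week 48, one at Week 60.
- n = 90, as written: S(48) = 86/90 = 0.9556. At Week 60 one participant is at risk and has the event, so S = 0. Incidence is 100% and the median is Week 60.
- n = 90, censored at the last assessment on NA: the risk set at Week 60 is 86, 64 or 56 if 0%, 25% or 35% of the 86 stop NA at Week 48 (25% to 35% is the planning range for the Arm 3 response rate in Protocol 9.2). Then 1 − 0.9556 × 85/86 = 5.6%; 1 − 0.9556 × 63/64 = 5.9%; 1 − 0.9556 × 55/56 = 6.2%. The median is not reached.
- n = 45: S(48) = 41/45 = 0.9111. As written, 100%. Aligned, with risk sets of 41, 31 or 27: 11.1%, 11.8% or 12.3%.
- Counting events only up to EOT: 4/90 = 4.4% or 4/45 = 8.9%, median not reached.

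**Step 3: the condition matters.** If the late event falls on day 340 while nine event-free participants have their EOT visit on day 345, ten are at risk and the curve reaches only 1/10 = 10%. The 100% result needs an event after the arm's last EOT day.

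**Step 4: how easily an arm is affected.** The chance of at least one such event is 1 − (1 − p)^m, with m event-free participants on NA after Week 48 and assumed follow-up risk p.

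| m | p = 0.5% | p = 1% | p = 2% |
|---|---|---|---|
| 86 (of 90) | 35% | 58% | 82% |
| 56 (of 90) | 24% | 43% | 68% |
| 41 (of 45) | 19% | 34% | 56% |

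**Step 5: the log-rank test.** A late event with only its own arm at risk adds nothing to the test (observed minus expected 0, variance 0). When both arms have late events, those events are compared among future cases only. A simulation of 10,000 trials had 90 per arm, two-sided 10% level, event risk before Week 48 of 10% vs 2%, and an equal assumed follow-up risk of 4%. It was unstratified, nobody stopped NA, the confirmation rule was left out, and event times were uniform within 0–48 and 48–96 weeks and moved to the next scheduled visit.

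| Rule | Rejection rate |
|---|---|
| As written | about 64% |
| Events up to EOT only | about 78% |
| Events and censoring to Week 96 | about 56% |

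The Monte Carlo standard error is about 0.5 points (√(0.64 × 0.36/10,000) = 0.0048).

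**The case against.** The strongest reply is that the author meant EOT as the end of observation for both events and censoring. The off-treatment rule in 5.4.14.2 has no EOT limit, so the limit looks deliberate, and a programmer could reasonably stop counting there. That stands as a plausible intention, and a reader should not infer that the plan certainly counts later events. But no passage cuts events at EOT, on-treatment is defined to include NA, and 5.4.15.1 summarises breakthrough by analysis phase, which leaves room for follow-up events. Two careful programmers could produce different curves.

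A reader might also infer that the written rule forfeits power for differences arising after Week 48 and that correcting it would restore this. That does not support the simple correction. With 5% risk before Week 48 in both arms and an assumed follow-up risk of 10% vs 2% (90 per arm), rejection is 10.6% as written, 11.8% with counting to EOT only and 48.5% with events and censoring to Week 96. Counting to EOT recovers none of that power, and the documents give no source for risks of that size.

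It is also fair that 5.4.14.2 and 5.4.11 require event and censoring counts by arm, so a curve at 100% beside a handful of events would be noticed. The counts would expose the error but not supply a correct curve or median.

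**Conclusion.** The defect is real on the literal text and minor. The 100% endpoint follows from the two rules alone, given one on-NA event after an arm's last EOT day. Its size in the example (100% against about 5.6% to 6.2% for n = 90) and the loss in the comparison of events before Week 48 (about 64% against 78% rejection) rest on assumed counts and risks. The documents give no on-NA event rate for this trial. For breakthrough the one comparable statement points low: Protocol 2.2.1 reports none in the earlier study's arms combining JNJ-6379 or placebo with NA.

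A wider reading, that the flare and breakthrough results as a whole are unsound, is not supported. Virologic and clinical flares are outside the problem. The protocol's endpoints are flare frequency and the breakthrough proportion, and neither uses these censoring rules. The primary and key secondary results are untouched. The affected analyses were added in the SAP and carry no multiplicity adjustment.

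**What to change.** State in 5.4.14.2 and 5.4.15.2 that only events on or before EOT count, and keep the EOT censoring. Later on-NA events stay in the incidence tables of 5.4.14.1 and 5.4.15.1. The cost is one sentence in each section and a change to the event derivation. The downside is that this gives no power for differences arising after Week 48.

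If those differences are of interest, add a separate analysis that counts events within the first continuous on-treatment period, NA included, and censors at the last assessment in that period. State with it that:
- stopping NA depends on response, so censoring at that point may be informative;
- events during NA re-treatment are left to the incidence tables, so counts will differ from them;
- it has less power for a difference confined to the period before Week 48 (about 56% in the scenario above).

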5.4.15. Virologic Breakthrough

5.4.15.1. Definition

HBV virological breakthrough is defined as having a confirmed on-treatment HBV DNA increase by $>1 \log_{10}$ from nadir level (lowest level reached during treatment) in participants who did not have on-treatment HBV DNA level below the lower limit of quantification (LLOQ) or a confirmed on-treatment HBV DNA level $>200 \text{ IU/mL}$ in participants who had on-treatment HBV DNA level below the lower limit of quantification (LLOQ). Confirmed HBV DNA increase/level means that the criterion should be fulfilled at 2 or more consecutive time points or at the last observed time point.

On-treatment will be defined as the time period in which the participant receives any of the study interventions (including NA).

The number and proportion of participants who experience a virologic breakthrough will be summarized descriptively by intervention arm and analysis phase.

The number and proportion of participants who experience a virologic breakthrough followed by on-treatment biochemical flare will be summarized descriptively by intervention arm.

5.4.15.2. Time to Virologic Breakthrough

Time to HBV virologic breakthrough will be defined as the number of days between the date of first study intervention intake and the date of the first occurrence of virologic breakthrough (i.e. the date of the first virologic breakthrough - the date of first study intervention intake +1). The participants who withdrew early from the study before experiencing virologic breakthrough or who did not experience virologic breakthrough will be censored at the last available HBV DNA assessment at or before EOT.

5.5. Exploratory Endpoints

5.5.1. Changes in Fibrosis

To explore the changes in the severity of liver disease at the end of follow-up versus screening/baseline, the changes in fibrosis (according to Fibroscan liver stiffness measurements) will be summarized using descriptive statistics (for example, may include n, mean, SD, 90% CI, median, minimum, maximum) by intervention arm. The comparison among intervention arms will

be done using ANCOVA with intervention arm, randomization stratification factors as main effects in the model and baseline score as covariate.

At each assessment time point, a frequency distribution of severity scores will be produced by intervention arm. A graphical display will also illustrate the findings.

Waterfall plots for changes from baseline of fibrosis will also be presented.

5.5.2. HBV RNA and HBcrAg

5.5.2.1. Values and Changes Over Time

HBcrAg will be summarized by treatment history (not currently treated and virologically suppressed) and overall, while HBV RNA will only be summarized by treatment history.

The values of and changes from baseline in HBV RNA and HBcrAg, respectively, will be summarized only descriptively over time in a similar manner as for values and changes from baseline over time in HBsAg, HBeAg, and HBV DNA as described in Sections 5.4.5.1, including the change from baseline value to nadir (i.e. maximum decrease for each participant) and the various graphical displays.

Waterfall plots for changes from baseline of HBV RNA and HBcrAg will also be presented.

5.5.2.2. HBV RNA Thresholds

The number and proportion of participants who meet the HBV RNA thresholds below during the study will be summarized descriptively by intervention arm and analysis phase over time.

Thresholds for **HBV RNA values**:

- < TND (target not detected)
- < LOD
- < LLOQ
- <1000 IU/mL

Thresholds for **HBV RNA decreases from baseline**:

- ≥ 1.0 Log IU/mL
- ≥ 2.0 Log IU/mL
- ≥ 3.0 Log IU/mL

5.5.2.3. HBcrAg Thresholds

The number and proportion of participants who meet the **HBcrAg** thresholds below during the study will be summarized descriptively by intervention arm and analysis phase over time.

Thresholds for **HBcrAg values**:

- < 3.0 LogU/mL

- < 4.0 LogU/mL

Thresholds for **HBcrAg** decreases from baseline:

- ≥ 1.0 Log U/mL
- ≥ 2.0 Log U/mL
- ≥ 3.0 Log U/mL

5.5.3. Time to Undetectability

The following time-to-event variables will be analyzed in a similar manner as for the time to event endpoints described in the Section [5.4.11](#).

5.5.3.1. Time to Undetectability of HBV DNA

Time to undetectability of HBV DNA is defined as the duration from the date of first study intervention intake to the date of the first occurrence of undetectability of HBV DNA (i.e. the date of the first occurrence of HBV DNA < LLOQ – the date of first study intervention intake + 1). The participant who did not achieve undetectability or who early withdrew from the study before achieving undetectability of HBV DNA will be censored at the last HBV DNA assessment before the date of withdrawal. Only the participants with HBV DNA \geq LLOQ at baseline will be included in this analysis.

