5.1. Inclusion Criteria

Each potential participant must satisfy all of the following criteria to be enrolled in the study:

- 1. Adult male or female participants 18 (or the legal age of consent in the jurisdiction in which the study is taking place) to 65 years of age, inclusive.
- 2. Participants must be medically stable, with the exception of HBV disease, on the basis of physical examination, medical history, vital signs, and 12-lead ECG performed at screening. If there are abnormalities, they must be consistent with the underlying illness in the study population. This determination must be recorded in the participant's source documents and initialed by the investigator.
- 3. Participants must have chronic HBV infection documented by serum HBsAg positivity at screening. In addition, chronicity must be documented by serum HBsAg positivity at least 6 months prior to screening or alternative markers of chronicity (HBeAg positivity or HBV DNA positivity at least 6 months prior to screening, ALT elevation above ULN at least 6 months prior to screening without another cause than HBV infection, liver

biopsy, or documented transmission event at least 6 months prior to screening).

Note: if documentation of chronicity (as mentioned above) at least 6 months prior to screening is not available, participants may be included if HBsAg positive and negative for immunoglobulin M (IgM) antibodies to HBc antigen at screening.

- 4. Participants who are **not currently treated** (defined as not having been on HBV treatment, including NAs and IFN products within 6 months prior to screening), including **treatment-naïve** participants (defined as never having received HBV treatment, including NAs and IFN products) should have:
 - a. Serum HBV DNA at screening ≥2,000 IU/mL for HBeAg-negative participants and ≥20,000 IU/mL for HBeAg-positive participants, AND
 - b. ALT levels at screening <10x ULN AND >ULN on two measurements at least 3 months apart (one of which is at screening).
- 5. Virologically suppressed participants should:
 - a. be on stable HBV treatment, defined as currently receiving NA treatment (ETV, TDF, or TAF) for at least 6 months prior to screening and having been on the same NA treatment regimen (at the same dose) as used in this study (see Section 6.1) for at least 3 months at the time of screening, AND
 - b. have serum HBV DNA <60 IU/mL on two measurements at least 6 months apart (one of which is at screening), AND

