4.2.2. Baseline Characteristics

For the viral activity parameters (e.g. HBeAg, HBsAg, HBV DNA, HBV RNA, HBcrAg, anti-HBs antibody, anti-HBe antibody), baseline values are used unless specified differently.

- Duration of HBV infection (Years) = (date of randomization – date of HBV infection +1)/365.25; rounded to 1 decimal
- Time since HBV diagnosis (Years) = (date of randomization – date of HBV diagnosis+1)/365.25; rounded to 1 decimal
- Mode of HBV infection: Sexual transmission, intravenously injectable drug use, blood transfusion, Hemophilia-associated injection, occupational exposure, mother to child transmission, unknown and other
- Treatment history: not currently treated, virologically suppressed
- History of IFN-alpha (All participants): Yes, No
- History of Lamivudine, Telbivudine, Adefovir (All participants): Yes, No
- Has never received HBV treatment (only for currently not treated participants): Yes, No
- Type of NA at study entry (only for virologically suppressed participants): TDF, TAF, ETV
- HBeAg status at screening: positive, negative
- HBeAg at baseline (quantitative): values in IU/mL and log10 IU/mL (for HBeAg positive participants only)
- HBsAg at baseline (quantitative): values in IU/mL and log10 IU/mL
- HBsAg category at baseline (quantitative: IU/mL):
 - Participants with HBsAg <500 IU/mL
 - Participants with HBsAg <1,000 IU/mL
 - Participants with HBsAg <10,000 IU/mL
 - Participants with HBsAg $\geq 10,000$ IU/mL
- HBV DNA at baseline (quantitative): values in IU/mL and log10 IU/mL
- HBV DNA category at baseline (quantitative: IU/mL):
 - Participants with HBV DNA < LLOQ (20 IU/mL) target detected (TD) or target not detected (TND)
 - Participants with HBV DNA < LLOQ (20 IU/mL) target detected
 - Participants with HBV DNA < LLOQ (20 IU/mL) target not detected

- Participants with HBV DNA < 60 IU/mL
- Participants with HBV DNA < 2,000 IU/mL
- Participants with HBV DNA < 20,000 IU/mL
- Participants with HBV DNA < 100,000 IU/mL
- Participants with HBV DNA \geq 100,000 IU/mL
- HBV RNA (quantitative): values in copies/mL and log10 copies/mL
- HBV RNA category at baseline (quantitative: copies/mL):
 - Participants with HBV RNA TND
 - Participants with HBV RNA < limit of detection (LOD)
 - Participants with HBV RNA < 1000 copies /mL
 - Participants with HBV RNA < LLOQ
 - Participants with HBV RNA \geq LLOQ
- Hepatitis B core related antigen (HBcrAg) at baseline (quantitative): values in log U/mL

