5.5.3.2. Time to Undetectability of HBV RNA

Time to undetectability of HBV RNA is defined as the duration from the date of first study intervention intake to the date of the first occurrence of undetectability of HBV RNA (i.e. the date of the first occurrence of undetectability of HBV RNA – the date of first study intervention intake + 1). The participant who did not achieve undetectability or who early withdrew from the study before achieving undetectability of HBV RNA will be censored at the last HBV RNA assessment before the date of withdrawal. Only the participants with HBV RNA values \geq LOD + 0.5 log 10 cp/mL (i.e. ≥ 2.99 log 10 cp/mL) at baseline will be included in this analysis.

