5.5.3.3. Time to Undetectability of HBcrAg

Time to undetectability of HBcrAg is defined as the duration from the date of first study intervention intake to the date of the first occurrence of undetectability of HBcrAg (i.e. the date of the first occurrence of HBcrAg < LLOQ – the date of first study intervention intake + 1). The participant who did not achieve undetectability or who early withdrew from the study before achieving undetectability of HBcrAg will be censored at the last HBcrAg assessment before the date of withdrawal. Only the participants with HBcrAg values \geq LLOQ + 0.5 Log10 U/mL (i.e. ≥ 3.5 Log10 U/mL) at baseline will be included in this analysis.

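### Time to HBV DNA undetectability has no margin between its entry and event thresholds, so suppressed participants just above 20 IU/mL can become events through measurement variation

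*SAP*

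**What the plan says.** SAP 5.5.3.1 takes participants with HBV DNA at or above the "LLOQ at baseline will be included in this analysis", whatever their treatment history. The event is "the date of the first occurrence of HBV DNA < LLOQ". No second value and no minimum fall is required. SAP 4.2.2 and Table 3 put the LLOQ at 20 IU/mL.

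Protocol 5.1, criterion 5b, requires suppressed participants to "have serum HBV DNA <60 IU/mL on two measurements at least 6 months apart (one of which is at screening". Criterion 4a requires at least 2,000 IU/mL (HBeAg-negative) or 20,000 IU/mL (HBeAg-positive) in participants not currently treated.

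The two sibling analyses set a margin. For HBV RNA (SAP 5.5.3.2) the baseline must reach "LOD + 0.5 log 10 cp/mL (i.e. ≥ 2.99 log 10 cp/mL) at baseline". For HBcrAg (SAP 5.5.3.3) it must reach LLOQ + 0.5 log10, which is 3.5 log10 U/mL.

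SAP 5.5.3 sends all three to the methods in SAP 5.4.11: Kaplan-Meier curves and medians by arm, a log-rank test, and a Cox model stratified by the two randomization factors. Stratification is stated only for the Cox model and the survival curves derived from it.

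**The concern.** The two treatment-history groups start from very different places. An untreated participant begins at least 2 log10 above the LLOQ (2,000/20 = 100-fold) and must have a real fall in viraemia to reach the event. A suppressed participant at 25 IU/mL needs only one reading slightly lower than the last, and has many visits at which to produce it.

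A Kaplan-Meier curve or log-rank test that pools the two mixes threshold crossings with true suppression. Crossings by chance occur in every arm, so their main effect is to blur arm differences and possibly shorten medians. They do not favour one arm.

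The pooling is also out of step with the rest of the SAP. Sections 5.4.5.1 and 5.4.5.4 report HBV DNA values and thresholds by treatment history, and the baseline HBV DNA subgroup in 2.4.1 is limited to untreated participants.

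**Working it through.** **The plan's own margins.** HBV RNA: LOD 2.49 + 0.5 = 2.99. HBcrAg: LLOQ 3.0 + 0.5 = 3.5. Both reproduce exactly. The same margin for HBV DNA is 20 × 10^0.5 = 63.2 IU/mL. The enrolment ceiling for suppressed participants is only log10(60/20) = 0.477 log10 above the LLOQ, so it lies just inside that margin.

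**Number of chances.** The Protocol 1.3.1 schedule has 15 post-baseline HBV DNA samples up to Week 48: Weeks 1, 2, 4, 6, 8, then every 4 weeks from 12 to 48.

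**Noise-only probability at a fixed true level.** With independent normal error on the log10 scale,

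P(event) = 1 − [1 − Φ((log10 20 − log10 level)/SD)]^15.

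Example: level 30 IU/mL, SD 0.10. z = (1.301 − 1.477)/0.10 = −1.76, Φ = 0.0391, and 1 − 0.9609^15 = 0.45. At 25 IU/mL and SD 0.05 the result is 0.33; at 40 IU/mL and SD 0.20 it is 0.64.

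**Noise-only probability across entrants.** Neither the within-person SD nor the distribution of true levels is in the documents, so both are assumptions. Participants were simulated with a constant true level, an observed screening value <60 and an observed baseline ≥20 IU/mL. Three level distributions were used: log-uniform 20-60, log-uniform 5-60, and lognormal with median 10 IU/mL and SD 0.4 log10. The ranges below run across the three.

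| Assumed SD (log10) | Event by Week 8, all entrants | Event by Week 48, all entrants | Event by Week 48, baseline 20-30 IU/mL | Event by Week 48 if two consecutive values required, all entrants | Entrants still included at ≥63.2 IU/mL |
|---|---|---|---|---|---|
| 0.05 | 10-23% | 16-31% | 43-56% | 6-17% | 1-2% |
| 0.10 | 22-43% | 34-56% | 69-83% | 13-33% | 3-5% |
| 0.15 | 35-60% | 55-75% | 79-92% | 21-47% | 6-10% |
| 0.20 | 48-72% | 72-86% | 86-96% | 30-60% | 9-15% |

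The 0.5 log10 margin therefore removes most of these entrants. Confirmation alone reduces the chance events but leaves a substantial share.

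**Size of the group.** The enrolment aim of 40% untreated gives 0.40 × 450 = 180 untreated and 270 suppressed. The share of suppressed participants at or above the LLOQ on Day 1 is not given. At an assumed 5% to 30% it is 14 to 81 people. If all 180 untreated participants qualify, that is 13.5/193.5 = 7% to 81/261 = 31% of the analysed set.

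**The case against.** A reader might infer that noise alone makes most of the suppressed entrants events. The documents do not support that as a fact, because they give no SD. Across all entrants it needs an SD of about 0.15 log10 or more. At 0.05 most would not reach the event by Week 48, so shortened medians are not assured.

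A reader might also suppose that the group is large. The only evidence in the documents points the other way: in the Phase 2a study described in Protocol 2.2.1, most suppressed participants on 75 mg were below quantification at baseline.

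Nor does the hazard ratio mix the groups. SAP 5.4.11 stratifies the Cox model by treatment history and plots its fitted curves by stratum. The problem is confined to the Kaplan-Meier curves, the medians and the log-rank test.

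Three further points stand in part:

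- An unconfirmed first occurrence is a convention the SAP uses for HBsAg, HBeAg, HBV RNA and HBcrAg as well. Only the missing margin is specific to HBV DNA.
- The HBV RNA margin sits on the LOD, and 2.99 is still below that assay's LLOQ of 4.04 log10 cp/mL. HBcrAg is the closer parallel.
- Protocol 2.3.1.2 expects the added drugs to deepen suppression, so a fall from 20-59 to below 20 IU/mL could be a drug effect. That argues for separating suppressed participants at least as much as for excluding them.

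Calling <LLOQ undetectability is a small labelling matter. Section 5.5.3.1 states the definition, and other sections report target detected and not detected separately.

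**Conclusion.** The point holds in limited form. SAP 5.5.3.1 leaves no gap between entry and event, admits suppressed participants within 0.48 log10 of the LLOQ, and departs from the margin used in the next two sections. Under the assumptions above (constant true level, independent errors, SD 0.05 to 0.20), 16% to 86% of such entrants could become events by Week 48 with no change in viraemia. Correlated errors between visits would lower these figures. Follow-up samples, which 5.5.3.1 does not exclude, would add chances.

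The effect on the trial is small. The analysis is exploratory and unadjusted for multiplicity, and no decision rule in the SAP depends on it. The listed time-to-undetectability endpoint (Protocol 3, SAP 1.1) names only HBV RNA and HBcrAg. This is a cheap improvement to the interpretability of the unstratified results.

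**What to change.** Amend SAP 5.5.3.1 in one of three ways:

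1. Require baseline HBV DNA of at least LLOQ + 0.5 log10 (about 63 IU/mL).
2. Restrict the analysis to participants not currently treated.
3. Keep the present entry rule, show the Kaplan-Meier curves and medians by treatment history, and stratify the log-rank test by it, in line with the SAP's other HBV DNA summaries.

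Optionally, require two consecutive values <LLOQ, dated at the first, and rename the endpoint as time to HBV DNA <LLOQ.

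The cost is SAP wording and a smaller or split analysis set; no new data are needed. Options 1 and 2 give up most or all of the information on low-level viraemia becoming unquantifiable in suppressed participants. Option 3 keeps it. Confirmation, if added, would make some reported times longer.
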